### 5.8.2.1 Dosing Schedule

The participants will be allocated to dosing group depending on the treatment schedule **and groups open at the time of randomisation**. Vaccination will be performed on Day 0, after eligibility has been reconfirmed, and on Day 28.

**Table 5 Overall Schedule of Assessments at Each Study Visit**

Visit/Call	Screen	Vaccination Clinic	Telephone Call	Clinic	Vaccination Clinic	Telephone Call	Clinic			End of Study / Early Discontinuation Clinic
	Day							Month		
Timepoint (window)	-42 to -1	0	1 (+1d)	7 (±1d)	28 (+2d)	29 (+1d)	35 (±1d)	3 (±7d)	6 (±7d)	9 (±7d)
Informed consent	X									
Baseline/eligibility variables										
Demographics	X									
Inclusion and exclusion criteria	X									
Height and weight	X									
Medical and disease history	X									
HIV, HCV, HBV (quantitative HBV DNA and quantitative HBsAg), HDV serology	X									
Urinalysis	X									
Urine drug screen	X									
Urine pregnancy test (β-hCG)	X	X [a]			X [a]			X [f]	X [f]	X
Laboratory eligibility and safety tests										
Haematology	X	X [a]		X	X [a]		X	X	X	X
Biochemistry	X	X [a]		X	X [a]		X	X	X	X
Liver function tests	X	X [a]		X	X [a]		X	X	X	X
Study vaccination										
Vaccination dose		X			X			X [g]		
Post-dose observation		X			X			X [g]		
Nivolumab dose (Group 3 and 4 only) [b]			✘		X					
Other safety assessments										

Visit/Call	Screen	Vaccination Clinic	Telephone Call	Clinic	Vaccination Clinic	Telephone Call	Clinic			End of Study / Early Discontinuation Clinic
	Day						Month			
Timepoint (window)	-42 to -1	0	1 (+1d)	7 (±1d)	28 (+2d)	29 (+1d)	35 (±1d)	3 (±7d)	6 (±7d)	9 (±7d)
Full physical examination	X	X [a]			X [a]			X [a]		X
Symptom-directed physical examination				X			X	X	X	
Vital signs	X	X		X	X		X	X	X	X
Local/systemic reactogenicity		X [c]	X	X	X [c]	X	X	X [c]		
Unsolicited adverse events [d]	X	X	X	X	X	X	X	X	X	X
Serious adverse events and adverse events of special interest	X	X	X	X	X	X	X	X	X	X
Prior and concomitant medications	X	X	X	X	X	X	X	X	X	X
Blood for HBV disease markers [e]		X [a]		X	X [a]		X	X	X	X
Immunogenicity assessments										
Blood for cellular immunogenicity assessments		X [a]		X	X [a]		X	X [a]	X	X

[a] Pre-vaccination on Day 0, Day 28, and Month 3 (for UK participants having an MVA-HBV boost)

[b] Participants in Group 3 will receive nivolumab on Day 28. ~~Group 4 is now closed only while Group 4 will receive nivolumab on Days 1 and 28.~~ The patients will be observed for 30 minutes after vaccination. If there are no safety concerns (vital signs and reactogenicity), nivolumab will be infused over 30 minutes and the patients will be observed in the study centre for a further 30 minutes post-infusion.

[c] Captured pre-vaccination and post-vaccination on Days 0 and 28, and Month 3 (for UK participants having an MVA-HBV boost) , via eDiaries for 7 days post-vaccination and then at the clinic assessment 7 days post-vaccination (Day 7 or 35)

### 6.3.2 Clinic Visits: Day 7, Day 35 and Month 3 + 7 Days (MVA-HBV Boost [UK participants only])

- Blood samples will be taken for immunogenicity assessments and HBV disease markers
- These visits should be anchored to the date of Vaccination and scheduled to occur 7±1 day after vaccination. If vaccination is administered on any day other than Day 28, the follow up visit should be scheduled 6-8 days after the date of actual vaccination. All other study visits after Day 0 (except day 35) are anchored to Day 0.**

### 7.1.5 Urine Pregnancy Test

A urine pregnancy test will be performed in female participants of childbearing potential at screening and confirmed to be negative pre-vaccination on Day 0 and 28 and at Month 3 if a booster dose of MVA-HBV is given (UK participants only), **and at Month 3 and 6 for those in Group 3 and 4**, as per local standard procedures and at each of the timepoints according to Table 2.

2.0 Change History

Version/Date	Change Log
1.0 16-Sep-2020	Created as new
1.1 19-Aug-2022	
Added partial AE imputation for determining if unsolicited AEs fall within 28 days of each vaccination
 
Changed the HBV DNA summary table from fold change from baseline to number and percentage of participants in each category
 
Removal of HBpgRNA and HBcrAg exploratory analyses
 
Addition of ICS and ELISpot definitions and analyses
 
Actual dose of nivolumab in mg/kg will be derived using baseline weight as weight is only collected at screening not at each visit
 
Added source of vital signs toxicity grading
 
Added visit windows for local/systemic reactogenicity
 
Updated list of laboratory parameters based on data received
 
Added list of DMC outputs to the appendix
 
Added laboratory toxicity grade appendix

1.2 09-Dec-2022	
Updated for Dry run 2 comments
 
Added HBsAg repeated measures analysis
 
Removed Kaplan-Meier analysis of HBeAg and HBsAg loss
 
Updated the seroconversion definitions
 
Added ICS and ELISpot analyses using non-parametric tests
 
Removed analyses for Month 3 boost (as no participants had the Month 3 boost)
 
Changed solicited AE analyses to combine the investigator (CRF) and eDiary data into a single analysis and removed the visit windowing for local/systemic reactogenicity
 
Added ALT and AST summary by time point

2.0 05-Jan-2023	
Up-versioned for signature
 
Updated ELISpot responder definition

4.0 Purpose

The Statistical Analysis Plan (SAP) describes the statistical methods to be used during the reporting and analyses of data collected under Protocol HBV002. This SAP only addresses primary, secondary, and select exploratory endpoints. All other exploratory endpoints to be analysed will be described in separate documentation.

5.0 Scope

The Statistical Analysis Plan outlines the following:

- Study Objectives
- Study Design
- Endpoints to be Analysed and the Analysis Sets (Estimands)
- Study Definitions
- Statistical Methods

6.0 Introduction

This SAP should be read in conjunction with the study protocol and electronic case report form (eCRF). Any further changes to the protocol or eCRF may necessitate updates to the SAP.

6.1 Changes from Protocol

The following changes in the planned analysis to the protocol have been done:

- The per-protocol analysis set will be a subset of the intent-to-treat analysis set instead of the safety analysis set as indicated in the protocol (due to data being summarised according to randomised treatment). In addition, instead of excluding all participants with major protocol deviations, only participants with major protocol deviations that could potentially bias trial analyses will be excluded
- With the exception of Alanine aminotransferase (ALT) and Aspartate aminotransferase (AST), which will include tables summarising results and changes from baseline for each time point, other laboratory measurements and all vitals sign variables will be listed only instead of being summarised using descriptive statistics as indicated in the protocol
- Shift tables of laboratory results, vital signs, and physical examinations will be summarised using the worst post-baseline result overall, rather than by time point as indicated in the protocol
- Line plots of laboratory results and vital signs over time will be presented by participants, rather than scatter plots of worst change from baseline as indicated in the protocol

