#### 10.2.2.6.2 Laboratory Safety Tests

Severity grading using the toxicity table in [Appendix 1](#) will be assigned to laboratory safety values where applicable. Laboratory results in reported units and standard international (SI) units will be listed, including high and low flags, severity grades where applicable, the corresponding normal range and clinical significance.

Laboratory safety tests summaries will be based on results in SI units. Absolute and change from baseline results, including the worst change for each variable for each participant will be summarised using descriptive statistics.

Treatment emergent out of range results with the corresponding severity grade, normal ranges, baseline results and clinical significance will be separately listed. Shift tables will be used to show changes from baseline at each timepoint and the worst change in each participant and scatterplots of the worst change will be produced. The number of participants showing shifts of at least two severity grades will be summarised.

The number of participants with treatment emergent clinically significant laboratory safety test results and laboratory safety test results of Grade 3 or 4 will be summarised.

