#### 10.2.2.6.3 Vital Signs

Absolute and change from baseline vital sign results, including the worst change for each variable for each participant will be summarised using descriptive statistics. Treatment emergent out of range results with the corresponding normal ranges, baseline results and clinical significance will be separately listed. Shift tables will be used to show changes from baseline at each timepoint and the worst change in each participant and scatterplots of the worst change will be produced. The number of participants with treatment emergent clinically significant results will be summarised.

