12.7.1 Primary Endpoints

The primary endpoints are:

- Safety and reactogenicity of the vaccine(s): incidence of AEs, SAEs, \geq Grade 3 study vaccine-related AEs within 4 weeks of vaccination
- Safety of the vaccines with nivolumab: incidence of AEs, SAEs, \geq Grade 3 AEs within 4 weeks of dosing
- Incidence of AESI
- Number and proportion of participants reporting TEAEs within each treatment group
- Number and proportion of participants within each treatment group with potentially clinically significant laboratory values and vital signs within each treatment group
- Change from baseline in laboratory tests and vital sign measurements to each time point of collection

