12.7.1.2 Laboratory Data

The number and percentage of participants with investigator assessed potentially clinically significant post-baseline values will be tabulated by laboratory category (haematology, biochemistry). Potentially clinically significant laboratory values as assessed by the investigator will be documented as AEs.

ALT and AST at each scheduled time point (Baseline, Day 7, Day 28, Day 35, Month 3, Month 6, and Month 9) and changes from baseline at each time point will be summarised by treatment group using descriptive statistics.

Haematology and biochemistry (including liver function tests) laboratory parameters listed in Table 6 will be presented using line plots of laboratory results by parameter and time point (including unscheduled visits) by participant.

Laboratory data values of the form of " $< x$ " (i.e., below the lower limit of quantification) or " $> x$ " (i.e., above the upper limit of quantification) will be imputed as " x " in the calculation of toxicity grading but displayed as " $< x$ " or " $> x$ " in the listings. Standard International (SI) units will be used for all laboratory parameters displayed in the figures and listings.

Table 6 Laboratory Tests

Category	Parameters
Haematology	leukocytes, basophils, basophils/leukocytes, eosinophils, eosinophils/leukocytes, lymphocytes, lymphocytes/leukocytes, monocytes, monocytes/leukocytes, neutrophils, neutrophils/leukocytes, haematocrit, haemoglobin, erythrocyte mean corpuscular haemoglobin, erythrocyte

Category	Parameters
	mean corpuscular haemoglobin concentration, erythrocyte mean corpuscular volume, erythrocytes, erythrocyte cell morphology, erythrocytes distribution width, platelets, fibrotest score, fibrotest stage, prothrombin intl. normalised ratio, prothrombin time, AST to platelet ratio index
Biochemistry (including liver function tests)	alanine aminotransferase, aspartate aminotransferase, gamma-glutamyl transpeptidase, alkaline phosphatase, bilirubin, direct bilirubin, urea nitrogen, creatinine, potassium, sodium, albumin, haptoglobin, alpha-2 macroglobulin, apolipoprotein A1
Urinalysis (dipstick)	specific gravity, pH, erythrocytes, protein, glucose, ketones, bilirubin, urobilinogen, leukocytes, nitrite
Urinalysis (drug screen)	amphetamine, barbiturates, benzodiazepine, cannabinoids, cocaine, methadone, opiate, phencyclidine, propoxyphene, tricyclic antidepressants
HBV disease markers	HBsAg, HBsAb, HBeAg, HBeAb, HBV DNA, HBcAb

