12.7.1.3 Vital Signs

Vital sign values will be considered potentially clinically significant if they meet either the low or high potentially clinically significant criteria listed in Table 7. The number and percentage of participants with any potentially clinically significant post-baseline value overall and by each criteria will be tabulated.

Table 7 Criteria for Potentially Clinically Significant Vital Signs

Vital Sign Parameter (unit)	Lower Limit	Upper Limit
Pulse rate (beats per minute)	< 45	> 130
Systolic blood pressure (mmHg)	< 80	> 155
Diastolic blood pressure (mmHg)		> 100
Temperature (°C)		≥ 39.0

A graphical display of each parameter by time point will be presented similarly to laboratory data.

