12.7.2.3 Laboratory Data

Laboratory values will be evaluated according to the Toxicity Grading Scale for Healthy Adult and Adolescent Volunteers Enrolled in Preventive Vaccine Clinical Trials (FDA) presented in Appendix 1. Derived toxicity grades are done based only on the numeric value of the parameter assessed.

The number and percentage of participants with each toxicity grade will be tabulated by baseline and maximum post-baseline worst result for each parameter and direction of change. Shift tables of laboratory results by worst change from baseline grade will be presented for the following parameters and direction of change:

- Haematology: leukocytes (low) [WBC decrease], leukocytes (high) [WBC increase], eosinophils (high) [eosinophils], lymphocytes (low) [lymphocytes decrease], neutrophils (low) [neutrophils decrease], haemoglobin (low) [haemoglobin], platelets (low) [platelets decrease], prothrombin time (high) [prothrombin time]
- Biochemistry: alanine aminotransferase (high) [alanine aminotransferase], aspartate aminotransferase (high) [aspartate aminotransferase], alkaline phosphatase (high) [alkaline phosphatase], direct bilirubin (high) [bilirubin increase], urea nitrogen (high) [blood urea nitrogen], creatinine (high) [creatinine], potassium (low) [hypokalaemia], potassium (high) [hyperkalaemia], sodium (low) [hyponatremia], sodium (high) [hypernatremia], albumin (low) [hypoalbuminemia]

Participants with any out of range values as determined using the central lab reference ranges will be listed.

All haematology, biochemistry, urinalysis, urine dipstick, and viral measurement results will be listed separately. In addition, investigator assessed clinically significant laboratory results (haematology, biochemistry, urinalysis) will be listed.

Pregnancy test results for female participants of childbearing potential will be listed.

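### Apart from ALT and AST, the primary endpoint of laboratory and vital-sign change from baseline at each time point has no planned group-level summary by time point.

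*SAP*

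**What the plan says.** The endpoint is the same in Protocol section 2, SAP 9.1 and SAP 12.7.1: "Change from baseline in laboratory tests and vital sign measurements to each time point of collection". It is one of six primary endpoints, under a primary objective of safety and reactogenicity.

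The protocol gave it a matching analysis. For laboratory tests (10.2.2.6.2): "Absolute and change from baseline results, including the worst change for each variable for each participant will be summarised using descriptive statistics". For vital signs (10.2.2.6.3): "Absolute and change from baseline vital sign results, including the worst change for each variable for each participant will be summarised using descriptive statistics". Both sections also planned shift tables at each time point.

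SAP 6.1 changes this. ALT and AST keep summaries of results and changes at each time point, but "other laboratory measurements and all vitals sign variables will be listed only instead of being summarised using descriptive statistics as indicated in the protocol". The next bullet moves the shift tables from each time point to the worst post-baseline result overall.

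The body of the SAP follows suit:

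- **ALT and AST (12.7.1.2):** values at each scheduled time point, and "changes from baseline at each time point will be summarised by treatment group using descriptive statistics".
- **Haematology and biochemistry parameters in Table 6 (12.7.1.2):** these "will be presented using line plots of laboratory results by parameter and time point (including unscheduled visits) by participant".
- **Vital signs (12.7.1.3):** "A graphical display of each parameter by time point will be presented similarly to laboratory data".
- **Laboratory grades (12.7.2.3):** "The number and percentage of participants with each toxicity grade will be tabulated by baseline and maximum post-baseline worst result for each parameter and direction". Section 12.7.2.4 treats vital signs in a similar way.

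**The concern.** The endpoint asks how each parameter moves from baseline at each visit. For everything except ALT and AST, the SAP removes both displays that could show this by group: the descriptive statistics by visit and the shift tables by visit. The endpoint itself is left unamended.

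Timing matters in this design. Groups 2 and 3 differ by nivolumab at Day 28, and Group 4 also receives it at Day 0. The Day 28 safety bloods are drawn before vaccination and the Day 35 bloods a week after it. Group summaries at those two visits would therefore bracket the second dose. A single worst grade over nine months cannot do so. A modest but consistent movement in one group that never reaches Grade 1 would have to be picked out by eye from individual line plots.

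**Working it through.** The plan gives no figure on this point. The check compares the endpoint with the planned outputs and counts parameters.

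**1. What each remaining display shows**

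| Display | By group? | By time point? | Change in value? |
|---|---|---|---|
| ALT/AST table (12.7.1.2) | yes | yes | yes |
| Line plots (12.7.1.2, 12.7.1.3) | no, by participant | yes | by eye only |
| Worst-grade tables (12.7.2.3, 12.7.2.4) | yes | no | grade only |
| Potentially clinically significant counts (12.7.1.2, 12.7.1.3) | yes | no | no |
| AEs within 28 days of each vaccination (12.7.1.1) | yes | by dose | only laboratory values recorded as AEs |

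Only the first row has all three features. The counts in the fourth row serve a separate primary endpoint, and for laboratory data they are tabulated by category (haematology, biochemistry), not by parameter.

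**2. How many parameters are affected**

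- SAP Table 6 has 25 haematology and 14 biochemistry entries: 25 + 14 = 39.
- Twelve of these are poor candidates for a change table: erythrocyte morphology (1), differentials as a share of leukocytes (5), and FibroTest score and stage, APRI, haptoglobin, alpha-2 macroglobulin and apolipoprotein A1 (6), which are not in the Protocol 7.1.4.1 or 7.1.4.2 panels. 39 − 12 = 27.
- Three more are also outside those panels: red cell distribution width, INR and the bilirubin entry other than direct bilirubin. 27 − 3 = 24.
- Counting from the protocol gives the same number: 14 numeric haematology tests in 7.1.4.1 and 10 biochemistry tests in 7.1.4.2. 14 + 10 = 24.
- With a planned summary of change by group and visit: 2 of 24 (ALT, AST). Without: 24 − 2 = 22. For vital signs: 0 of 4.

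Protocol 6.1 and 6.3.4 mention prothrombin time only at screening and Month 9, so its table may have a single post-baseline row.

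**3. What the worst-grade tables cover**

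The 12.7.2.3 shift list names 7 haematology and 9 biochemistry parameters, 16 in all, each among the 24. The other 24 − 16 = 8 are haematocrit, erythrocytes, MCV, MCH, MCHC, monocytes, basophils and GGT. None of these has a grade in SAP Appendix 1, so they have no parameter-level group table at all.

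**4. What a grade table can miss (assumed values, for illustration only)**

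- Platelets falling from 200 to 145 ×10³/µL: (200 − 145)/200 = 27.5%. Grade 1 begins at 140, so the result stays Grade 0.
- Creatinine rising from 0.8 to 1.4 mg/dL: (1.4 − 0.8)/0.8 = 75%. Grade 1 begins at 1.5, so the result stays Grade 0.
- Haemoglobin is an exception: Appendix 1 also grades its decrease from baseline, starting with any decrease above 0.

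**The case against.** The best defence is that the SAP declares the change openly, the study is open-label and mostly descriptive, and no test or decision rule uses these summaries. The groups are also small: 10 and 9 in the closed Groups 1 and 4, and about 16 planned in each of Groups 2 and 3. Plots of every participant over time can be informative at that size, and a uniform move as large as those illustrated would probably be visible in them.

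Much of this stands and limits the point. It does not remove it. Declaring a changed analysis does not amend the endpoint, which 12.7.1 still lists. Unlike the first bullet of 6.1, this one gives no reason. Nor can group size be the reason, because ALT and AST get tables by visit in the same groups.

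Three stronger readings are tempting, and the documents do not support them:

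- **That the endpoint has no group-level result.** ALT and AST have change tables by group at every scheduled visit. These tests also feature in the protocol's holding criteria and in the Safety Monitoring Committee's ad hoc review.
- **That everything else is only listed, or that laboratory toxicity has no timing.** Shift tables and clinically significant counts remain. Laboratory values the investigator judges potentially clinically significant are documented as AEs, and AEs are tabulated separately within 28 days of each vaccination. The gap concerns changes below that level.
- **That 37 of 39 parameters lose a summary they should have.** Twelve of the 39 are descriptive, duplicate or non-panel entries. The protocol's own panels give the fairer count, 22 of 24.

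**Conclusion.** The point holds in limited form. The primary endpoint is answered by group and visit for ALT and AST only. The remaining 22 of 24 protocol-panel numeric laboratory tests and all 4 vital signs have no planned group summary of change at any time point, and 8 of the 22 also lack a worst-grade table.

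The count rests on reading Protocol 7.1.4.1 and 7.1.4.2 as the scheduled panels. The platelet and creatinine figures are assumed values that show what the grading cannot see; they do not predict what will happen.

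The data are collected and listed, and no inferential conclusion depends on these tables. The defect is a declared mismatch between a primary endpoint and its analysis. It should be corrected, but it does not threaten the validity of the trial.

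**What to change.** Amend the second bullet of SAP 6.1. Do not delete it, because it carries the ALT/AST provision and declares the departure from the protocol.

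In 12.7.1.2 and 12.7.1.3, extend the ALT/AST table (observed value and change from baseline, by group and scheduled visit) to:

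- the numeric haematology and biochemistry parameters in Protocol 7.1.4.1 and 7.1.4.2, including GGT and direct bilirubin;
- pulse rate, systolic and diastolic blood pressure, and temperature, with separate rows for the readings before and after vaccination on vaccination days.

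Limiting the extension to the 12.7.2.3 shift list would not be enough, since that list omits GGT and seven other scheduled tests.

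Keep in 6.1 a declared list of the Table 6 entries that stay listed only, with the reason: for example erythrocyte morphology, percentage differentials, and the FibroTest and APRI items used at screening.

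The cost is SAP wording and an existing table layout repeated for 22 + 4 = 26 further parameters, so more output pages and no new data. If the sponsor does not want those pages, the weaker alternative is to narrow the endpoint wording to what will be summarised and give the reason in 6.1.
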